8. EXPLORATORY LABORATORY RESEARCH STUDIES

8.1 Collecting, tracking and disposition of samples

Intended use: During the course of participating on this study, 60 cc of blood (3 ml/kg not to exceed 60 ml of blood for pediatric subjects) at baseline and at landmark visits at 3, 6, 12 months and annually thereafter, and 5 cc of bone marrow aspirate (baseline, 3 months, 6 months, 12 months, and annually thereafter) will be obtained for the following correlative laboratory research studies. Up to an additional 10 cc of blood (3 ml/kg not to exceed 10 ml of blood for pediatric subjects) may be collected during follow up every 1-6 months (according to how often they get their counts checked) for correlative laboratory studies. The protocol will cover shipment materials/costs for these additional samples to be returned to the NIH since they are for research use (no results given). Baseline samples may be obtained on another protocol, such as 04-H-0012. These studies are not used in assessing the primary endpoint but are undertaken as descriptive or exploratory ancillary studies. Some or all may be performed on each subject, and they may be correlated with response.

- Thrombopoietin level
- CD34 cell number in whole blood and bone marrow aspirate by flow cytometry
- T cell receptor V-beta profile in the marrow and peripheral blood
- Extended peripheral blood flow cytometric phenotyping for cell surface or intracellular proteins
- Evaluation for the presence of abnormalities of the telomere repair complex including telomere length and genetic testing of genes associated with the telomere repair complex
- Evaluation for the presence of abnormalities of genes associated with hematopoiesis, via genetic testing or gene expression analysis
- Evaluation for the presence of abnormalities of genes associated with inherited bone marrow failure
- Serum cytokine, chemokines and soluble receptor levels
- Serum (or plasma) and cells for viral analyses

- Hematopoietic progenitor colony, long term-culture-initiating cell, and immunodeficient mouse engraftment assays for primitive cell content and function
- Pharmacokinetic studies of eltrombopag kinetics in Cohort 1 and extension cohort starting with subject # 120 (Appendix D). Pharmacokinetic sampling will not be collected for Exploratory Laboratory Cohort.
- Single cell RNAseq on bone marrow specimens to detect chromosomal aneuploidy before and after treatment
- Telomere length on peripheral blood leukocytes by flow-FISH before and after treatment
- In the event there is any extra sample, these will be stored with the subject's permission for other exploratory laboratory research studies reviewed and approved by the IRB and listed in Appendix B.

Storage: Research samples will be stored coded in the secure laboratory of [name].

Tracking: Samples will be ordered and tracked through the CRIS Research Screens. Should a CRIS screen not be available, the NIH form 2803-1 will be completed and will accompany the specimen and be filed in the medical record. Specimens will be entered in the NHLBI Biospecimen Inventory System (BSI). Bone marrow samples obtained for cytogenetic studies will be submitted to Quest Laboratories under a fee-for-service contract. Coded/linked biospecimens to be shared outside of NIH for future research use requires an executed Material Transfer Agreement (MTA) and may require IRB approval if results will be returned and re-identified. Identifiable samples will not be sent outside of NIH without IRB approval and an MTA.

End of study procedures: Samples from consenting subjects will be stored until they are no longer of scientific value or if a subject withdraws consent for their continued use, at which time they will be destroyed.

Loss or destruction of samples: Should we become aware that a major breech in our plan for tracking and storage of samples has occurred, the IRB will be notified.

9. BIOSTATISTICAL CONSIDERATIONS

9.1 Sample sizes

The statistical section of this protocol has been amended to first (**amendment B**) increase the accrual ceiling to 31 subjects from 25 subjects to increase the likelihood to have at least 25 evaluable subjects at the 6-month time point for analysis. Next, with **amendment (8), submitted on August 22, 2013**, to add a second cohort with a reduced eltrombopag schedule while keeping the primary endpoints unchanged. Next, with **amendment (16), submitted on October 2, 2014**, to add a third cohort revising the administration schedule to allow for h-ATG, CsA, and eltrombopag to all be administered starting Day 1 while keeping the primary endpoints unchanged. Eltrombopag will be administered for 6 months and the primary endpoint will remain the same, response at month 6.

Our past experience with h-ATG/CsA suggests that the CR probability at 6 months for previously untreated patients given this regimen is approximately 10%~12%. Our data supports that among those in which a CR is observed, evolution to monosomy 7 and leukemia did not occur. Therefore, CR will be used as a surrogate for late events for the purpose of study design. We hypothesize that the actual CR probability using this treatment would reach 30% or more and a CR probability of 10% or less would warrant terminating the treatment on this patient population. Let p be the CR probability at 6 months for this patient population.

In the **original protocol, approved on June 13, 2012**, our sample size was determined by testing the null hypothesis, $H_0: p \leq 10\%$, versus the alternative, $H_1: p \geq 30\%$, at 0.05 significance level and 0.80 of the power. We intended to test this treatment using a small number of patients, and terminate the study if early evidence suggests that the CR probability fell below the benchmark rate of 10%. We determined the sample size using the Two-Stage Minimax Design of Simon (1989), since it required a smaller total number of subjects ($n=25$) compared to the Two-Stage Optimal Design ($n=29$). At the first stage, 15 subjects would be accrued and the null hypothesis would be accepted (i.e., the treatment would be terminated) if no more than 1 subject had a CR to the treatment within 6 months. If 2 or more subjects had a CR to the treatment within 6 months at the first stage, 10 additional subjects would be accrued. The null hypothesis of $p \leq 10\%$ would be accepted if the total number of patients having CR within 6 months was 5 or less.

With amendment B, approved on December 3, 2012, we increased the accrual ceiling to 31 subjects from 25 subjects to increase the likelihood to have at least 25 evaluable subjects at the 6-month time point for analysis of secondary endpoints while maintaining the statistical power for the primary endpoint of the study. This modified the statistical design as follows: Let p be the CR probability at 6 months for this patient population. Our sample size is determined by testing the null hypothesis, $H_0: p \leq 10\%$, versus the alternative, $H_1: p \geq 30\%$, at 0.05 significance level and 0.865 for power. We would like to test this treatment using a small number of patients, and terminate the study if early evidence suggests that the CR probability falls below the benchmark rate of 10%. We determine the sample size using the Two-Stage Minimax Design of Simon (1989), since it requires a smaller total number of subjects ($n=31$) compared to the Two-Stage Optimal Design ($n=34$). At the first stage, 24 subjects will be accrued and the null hypothesis will be accepted (i.e., the treatment will be terminated) if no more than 2 subjects demonstrate a CR to the treatment within 6 months. If 3 or more subjects have a CR to the treatment within 6 months at the first stage, an additional 7 subjects will be accrued. The null hypothesis of $p \leq 10\%$ will be accepted if the total number of subjects having a CR within 6 months is 6 or less. The “ph2simon” function in the “Clinfun” package “Clinical Trial Design and Data Analysis Function, Version 1.0.5” of the statistical software R was used to compute the numerical results of the Two-Stage Design.

The current pilot study design has a cohort of 31 subjects receiving eltrombopag starting day 14 and ending at the 6 month time point (cohort 1). With **amendment (8), submitted on August 22, 2013**, once accrual to cohort 1 has been completed without reaching any study stopping rules we propose to treat another cohort (cohort 2) of 33 subjects whereby they would be treated with the same regimen except that they would receive a reduction in exposure to eltrombopag from 6 to 3 months. The primary and secondary endpoints, objectives, eligibility, statistics, including sample size and stopping rules, monitoring and ancillary studies apply the same way for cohort 2 as for cohort 1. With amendment 16, submitted on October 2, 2014, once accrual to cohort 2 has been completed without reaching any stopping rules we propose to treat another cohort (cohort 3) of 31 subjects whereby they would be treated with the same regimen except that they would start h-ATG, CsA, and eltrombopag on Day 1. Eltrombopag will be administered up to the 6-month landmark visit. The primary and secondary endpoints, objectives, eligibility, statistics, including sample size and stopping rules, monitoring and ancillary studies apply the same way for cohort 3 as for cohorts 1 and 2 with the exception of one additional secondary objective (relapse rate between month 6 to month 24 when receiving low CsA during this time period).

	Sample size (n)	Eltrombopag	Primary Efficacy Endpoint	Statistical Design
Cohort 1	31	D 14 – 6 months	CR rate at 6 months	Simon Two-Stage
Cohort 2	33	D14 – 3 months	CR rate at 6 months	Simon Two-Stage
Cohort 3	31	D1 – 6 months	CR rate at 6 months	Simon Two-Stage

Starting with Amendment V, an extension cohort was added of 55 subjects in order to have data to improve precision of exploratory analysis of secondary endpoints, and to obtain more pharmacokinetic data on the

combined regimen. Then with Amendment FF, the extension cohort ceiling is raised to 87 subjects with the aim of having an additional 32 subjects to provide fresh research samples for 1) detection of cytogenetic abnormalities by single cell RNAseq methods in our laboratory, 2) measurement of telomere length before and after treatment by flow-FISH, and 3) additional pharmacokinetic data. The entire extension cohort (n=87) will be included in the analysis of secondary endpoints, but not in the primary endpoint analysis of cohort 3. We plan to use descriptive statistics, not hypothesis testing, in the analysis of the extension cohort.

In this revision, we have estimated our sample size (n=32) on the need for fresh samples for ancillary studies. Specifically, using our newly developed method to detect clonal evolution using RNAseq (will provide manuscript), we predict that we will require at least 3 patient samples with clonal evolution. We estimate that between 10% to 40% of patients will clonally evolve (Townsley et al. NEJM 2017). Assume that the expected proportion of patients with clonal evolution is 21%. Based on the exact calculation using Binomial distributions, the requested sample size of (n=32) will lead to a probability of 97.6% to obtain 3 or more samples. The true proportions of clonal evolution and their precision will be estimated using sample proportions, standard errors and confidence intervals.

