3. STUDY DESIGN

[figure not shown]
This study is designed as a non-randomized, pilot phase I/II study in which 182 subjects with severe aplastic anemia who have not received prior definitive immunosuppressive therapy will be treated with a standard regimen of h-ATG/CsA, combined with eltrombopag as experimental therapy. The first 31 subjects will be enrolled to cohort 1. Then up to 33 subjects will be enrolled to cohort 2 while up to 31 subjects will be enrolled in cohort 3. Subjects enrolled to cohort 1 will receive eltrombopag for 6 months whereas subjects enrolled to cohort 2 will receive eltrombopag for 3 months. Subjects enrolled in cohort 3 will initiate h-ATG, CsA and eltrombopag on Day 1. The primary clinical endpoint of this study is the quality of hematologic response at 6 months. In cohorts 1 and 2 eltrombopag will be initiated on day 14 to avoid overlap with the known transient hepatotoxicities associated with ATG and cyclosporine. Cohort 3 will initiate h-ATG, CsA, and eltrombopag on Day 1 if there are no significant hepatotoxicities seen in cohorts 1 and 2. Patient-reported outcome questionnaires (Appendix E) will be collected initially when the subject enrolls on-study (pre-ATG/CSA), pre-eltrombopag, at 3 and 6 months, and annually for 5 years.

Up to an additional 87 subjects may be enrolled into the Extension Cohort in order to allow subjects to be enrolled and treated while a new SAA treatment naïve protocol is developed and approved. In addition, 25 subjects will be enrolled for Laboratory Exploratory Cohort. The treatment schedule for both the Extension & Laboratory cohorts will be the same as Cohort 3.

Protocol Design for Cohort 1

[figure not shown]

Protocol Design for Cohort 2 added August 2013

[figure not shown]

*Cohort 2 will continue CsA administration month 6 to month 24 at 2.0mg/kg per amendment number 15

Protocol Design for Cohort 3 added September 2014

Protocol Design for Extension Cohort and Laboratory Exploratory Cohort

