9.2 Statistical Methods

For each cohort, the planned analyses will include descriptive statistics on the proportions of responses (% subjects with partial or complete response), cumulative incidence of response with death considered to be a competing risk and the time to complete response. The response probabilities, including complete response probability and partial response probability, will be estimated using the sample proportions, and their inferences, including confidence intervals and hypotheses testing, will be evaluated using Binomial distributions. Survival analysis will include methods based on Kaplan-Meier estimates and Cox regression. Although we have a small sample size, if it is appropriate, we will consider additional analyses for the primary and secondary endpoints using the analysis of variance, multiple regression and logistic regression models. Graphical tools will be used to display the appropriate estimates (i.e. estimated proportions and Kaplan-Meier curves) and their corresponding 95% confidence intervals.

Results for each cohort will be compared separately to the historical data from the large numbers of patients treated at the NIH previously with either a single or repeat course of immunosuppression from prior NHLBI studies: the h-ATG/CsA protocol (90-H-0146); the h-ATG/CsA vs. Cytoxin/CsA protocol (97-H-0117); the h-ATG/CsA/MMF protocol (00-H-0032); the h-ATG/CsA/Rapamune protocol (03-H-0193); the r-ATG vs. alemtuzumab protocol (03-H-0249); and h-ATG/CsA vs. r-ATG/CsA protocol (06-H-0034). More specifically, results from the current trial will be compared to our large historical experience with a horse ATG based regimen in nearly 400 patients (from the aforementioned studies) of a hematologic response rate of 60-70%, a complete response rate of 10-15%, a relapse rate of 30-40%, a clonal evolution rate (any clonal abnormality) of 15-20%, and a high risk evolution rate (to monosomy 7, high risk MDS, leukemia, or complex cytogenetics) of 10-15%.

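### The historical control in sections 9.2 and 9.4 is not limited to first-course horse-ATG patients, so it does not match the population this trial enrols

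*Combined protocol and SAP*

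**What the plan says.** Section 3 describes a "non-randomized, pilot phase I/II study". There is no randomised or concurrent comparison arm.

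Section 4 considers only patients who have had no ATG-based immunosuppression, and exclusion 4.2.3 rules out prior ATG, alemtuzumab or high-dose cyclophosphamide. The design benchmark in 9.1 is for the same kind of patient: "the CR probability at 6 months for previously untreated patients given this regimen is approximately 10%~12" (per cent).

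Section 9.2 then defines the historical comparator in two sentences. The first compares each cohort separately with "patients treated at the NIH previously with either a single or repeat course of immunosuppression from prior NHLBI studies" and lists six protocols, among them "the r-ATG vs. alemtuzumab protocol (03-H-0249"). The second is more specific. It names "our large historical experience with a horse ATG based regimen in nearly 400 patients (from the aforementioned studies") and gives benchmark rates, including "a complete response rate of 10-15" per cent.

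Section 9.4 plans response and toxicity comparisons against the same six protocols. It limits them neither to horse ATG nor to a first course, and it does not say whether the arms of a protocol are pooled or kept apart.

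**The concern.** With no concurrent control, the historical set carries every comparative statement the trial can make. The protocol already makes one: 2.9.1 calls the 6-month overall response in the first patients (11 of 13) higher than in historical data, and says the results can inform a randomised phase III design.

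Two features of the comparator do not fit that use. A patient receiving a repeat course could not have entered this trial if the earlier course was one of those named in 4.2.3. And several listed protocols include arms that are not the standard regimen to which eltrombopag is being added. If such patients count as control, a difference may reflect prior treatment or a different immunosuppressant, not eltrombopag.

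**Working it through.** **Step 1. Can the plan's benchmark be reproduced?** Not from the documents: they give no patient counts by course, arm or ATG type. It can only be checked for agreement between sections. Section 9.2 gives response 60-70%, CR 10-15% and relapse 30-40%. Section 2.3.2 gives 60-70% response for ATG plus CsA and 10-15% CR for h-ATG, and the Precis gives 30-40% relapse. These agree. The 9.1 CR range is narrower (10-12%) and is tied to 6 months and to previously untreated patients; the 10-15% range carries no time point.

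**Step 2. Trial population against comparator.**

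| Feature | Trial (4, 4.2.3) | Benchmark in 9.1 | 9.2, first sentence | 9.2, second sentence | 9.4 |
|---|---|---|---|---|---|
| Prior ATG-type therapy | none allowed | previously untreated | single or repeat course | not restricted | not restricted |
| Backbone | h-ATG/CsA | h-ATG/CsA | all six protocols | horse-ATG based | all six protocols |

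The second sentence of 9.2 repairs the backbone row but not the prior-therapy row. Section 9.4 repairs neither.

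**Step 3. The six protocols, as 9.2 describes them.**

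| Protocol | Regimens named | Non-horse-ATG arm? |
|---|---|---|
| 90-H-0146 | h-ATG/CsA | no |
| 97-H-0117 | h-ATG/CsA vs cyclophosphamide/CsA | yes |
| 00-H-0032 | h-ATG/CsA/MMF | no |
| 03-H-0193 | h-ATG/CsA/sirolimus | no |
| 06-H-0034 | h-ATG/CsA vs r-ATG/CsA (three arms according to 9.4) | yes |
| 03-H-0249 | r-ATG vs alemtuzumab | yes; no horse-ATG arm named |

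Three of six have a non-horse-ATG arm, and one of those three names no horse-ATG arm.

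**Step 4. Direction of any bias.** Let h be the rate in first-course horse-ATG patients, q the rate in other patients counted as control, and f their share. The control rate becomes (1 − f)h + fq, a shift of f(q − h).

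- Response, rabbit ATG or alemtuzumab: 2.3.2 reports inferior response, so q − h < 0. The control rate falls, which favours eltrombopag.
- Toxicity, cyclophosphamide: 2.3.2 says the NHLBI trial against ATG plus CsA was stopped early for toxicity, fungal infections and deaths in the cyclophosphamide group, so q − h > 0 for adverse outcomes. The control looks worse, which favours eltrombopag.
- CR, cyclophosphamide: 2.3.2 gives 40-50% against 10-15%, so q − h lies between 40 − 15 = 25 and 50 − 10 = 40 points. The control rate rises, which works against eltrombopag.
- Repeat courses: the documents give no response rates by course, so neither sign nor size can be derived.

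The share f is not given for any group, so no shift can be calculated.

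**The case against.** **The 9.2 benchmark is already restricted to horse ATG.** This stands. A reader might infer that the 10-15% CR and 60-70% response figures are diluted by rabbit-ATG, alemtuzumab or cyclophosphamide patients. The documents do not support that: the sentence giving them names a horse-ATG based regimen, and the figures agree with those quoted for it elsewhere. The restriction says nothing about repeat courses, though, and does not reach 9.4.

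**Section 9.4 never says that arms will be pooled or called the control.** This is also correct. It lists protocols separately and names arms in some of them. But it does not say that arms are kept apart, and 03-H-0249 could contribute no horse-ATG control on its own description. The risk is an undefined comparison, not a stated error.

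**Repeat-course records may serve a different purpose.** Endpoint (f) in 9.4 concerns response after relapse and re-treatment, and such records could be meant for it. Section 9.2 does not say so; it compares each cohort's results in general.

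**The Simon design.** Because 10% is the lowest value of both stated CR ranges, a reader might infer that the decision rule in 9.1 is defective or claims superiority over h-ATG/CsA. The documents do not support that. Section 9.1 states the null openly: "a CR probability of 10% or less would warrant terminating the treatment on this patient population". The final rule, under which the null "will be accepted if the total number of subjects having a CR within 6 months is 6 or less", gives a type I error of 0.0305 at 10% and power of 0.8651 at 30%, consistent with the stated 0.05 and 0.865. Passing is nowhere described as proof of superiority, and 9.2 plans binomial confidence intervals. The rule does not use the historical set and needs no change.

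**Conclusion.** The comparator is mis-specified in two places. Section 9.2 admits repeat-course patients although the trial and the 9.1 benchmark concern patients without prior ATG-type treatment. Section 9.4 has neither a first-course nor a horse-ATG limit, and three of its six protocols contain an arm without horse ATG.

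The likely directions differ by endpoint: favourable to eltrombopag on response (rabbit ATG, alemtuzumab) and on toxicity (cyclophosphamide), unfavourable on CR (cyclophosphamide). These directions assume that the arms in question would actually be used as control, which the plan leaves open. The net size cannot be determined, and nothing here shows that any stated benchmark figure is wrong. The point is worth acting on because the historical set is the trial's only comparator and the correction is cheap. The primary decision rule, sample size and power are unaffected.

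**What to change.** In 9.2, remove the reference to repeat courses and define the control as first-course, ATG-naive patients (prior therapy as in 4.2.3) treated with horse-ATG/CsA-based regimens:

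- keep 90-H-0146, 00-H-0032 and 03-H-0193;
- keep only the h-ATG arms of 97-H-0117 and 06-H-0034;
- drop 03-H-0249.

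That leaves five of the six protocols, three whole and two in part, all subject to the first-course restriction. Keeping the MMF and sirolimus protocols is reasonable for response, since 2.3.2 reports that neither addition improved results.

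In 9.4, refer to this 9.2 set for both response and toxicity. Report the number of patients kept from each protocol. If non-horse-ATG arms or repeat courses are shown, show them separately and do not label them as control.

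Because much of the outcome data is already in hand (2.9.4 reports 178 of 182 accrued), select records by eligibility, course and arm only, never by outcome, and date the change.

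Cost: a few sentences in 9.2 and 9.4, and a selection among records of earlier NHLBI studies, assuming course and arm are recorded for each patient. The historical set becomes smaller and its estimates less precise, by an amount the documents do not allow to be calculated. No new patients or procedures are needed.

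### Does the Simon rule's count of complete responses *within* 6 months test a different event from the primary endpoint, CR *at* 6 months?

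*Combined protocol and SAP*

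**What the plan says.** Under the Amendment B design in section 9.1, 24 subjects enter stage 1. The treatment is stopped "if no more than 2 subjects demonstrate a CR to the treatment within 6 months". The condition for going on to stage 2 is worded in the same way: "If 3 or more subjects have a CR to the treatment within 6 months at the first stage", then 7 more enter, for 31 in total. At the end, the null hypothesis "will be accepted if the total number of subjects having a CR within 6 months is 6 or less". All three counts therefore use *within*.

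The same paragraph defines the parameter: "Let p be the CR probability at 6 months for this patient population". The 10% null comes from past experience that is also timed at month 6: section 9.1 reports that "the CR probability at 6 months for previously untreated patients given this regimen is approximately 10%~12" per cent. The opening of 9.1 says, when adding Cohort 3, that "the primary endpoint will remain the same, response at month 6". The cohort table in 9.1 lists the CR rate at 6 months beside the Simon two-stage design for Cohorts 1, 2 and 3, and section 9.3 names the CR rate at 6 months as the primary efficacy endpoint.

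The rule reaches the later cohorts because 9.1 says that the "statistics, including sample size and stopping rules, monitoring and ancillary studies apply the same way for cohort 3 as for cohorts 1 and 2".

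**The concern.** Section 7 sets response landmarks at 3 and 6 months, so a CR can be on record before month 6. If such a CR were lost by month 6, the two wordings would classify the subject differently: a success under *within*, a failure under *at*. Sections 9.3 and 5.7 make non-responders of dropouts, of subjects who fail to respond and move to alternative therapy, and of Cohort 2 subjects re-treated before month 6. No sentence deals with a subject who slips from CR to partial or no response without one of those events.

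The difference runs one way. The literal count can never be below the month-6 count, so any disagreement favours continuing past stage 1 or declaring activity. The type I error was computed against a 10% benchmark for CR at 6 months. Applying the same cut-offs to a more generous event would make the test more liberal than stated, in a rule that decides both stopping and the claim of activity.

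**Working it through.** **Inputs (section 9.1).** p0 = 10%, p1 = 30%; n1 = 24, stop at 2 or fewer; n = 31 (n2 = 7), accept the null at 6 or fewer; significance level 0.05, power 0.865.

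**Step 1: reproduce the plan's figures, counting CR at 6 months.** With X1 ~ Bin(24, p) and X2 ~ Bin(7, p),

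P(reject) = Σ over x from 3 to 24 of P(X1 = x) × P(X2 ≥ 7 − x).

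- At p = 0.10: P(X1 ≤ 2) = 0.564 and P(reject) = 0.0305.
- At p = 0.30: P(X1 ≤ 2) = 0.012 and P(reject) = 0.8651, which matches the stated 0.865.

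A search over designs at these settings also returns the stated minimax total of 31 and optimal total of 34. The published operating characteristics are correct for the month-6 count.

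**Step 2: what the literal count would do.** Let t be the probability of a CR that is recorded before month 6, is lost by month 6, and is not already a non-response under 9.3 or 5.7. The documents give no value for t, so the values below are assumptions. With a true month-6 CR rate of 10%, the literal count has success probability 0.10 + t. Its rejection probability comes from the Step 1 formula at 0.10 + t. The chance that the two counts disagree comes from exact trinomial enumeration (CR at month 6, CR lost, neither).

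| t (points) | share of counted CRs lost, t/(0.10 + t) | P(reject), literal count | P(literal rejects, month-6 count does not) | P(stage 1 continues only through lost CRs) |
|---|---|---|---|---|
| 0 | 0% | 3.05% | 0% | 0% |
| 0.5 | 4.8% | 3.85% | 0.8% | 3.3% |
| 1.0 | 9.1% | 4.77% | 1.7% | 6.5% |
| 1.1 | 10.0% | 5.0% | 2.0% | 7.2% |

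The 5% level is reached at a counted rate of 11.1%, that is 11.1 − 10 = 1.1 points. The design has this slack because its actual type I error, 3.05%, is below the nominal 5%. At an assumed 2 points the figure would be 7.04%. Disagreement in the other direction has probability zero.

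**Step 3: which end of the range the documents suggest.** Section 2.9.2 reports that Cohort 2 subjects, who stop eltrombopag at 3 months, had all maintained or normalized their counts between months 3 and 6. Section 5.2 places the unexpected relapses after the 6-month visit. Both point towards t near zero.

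**Step 4: which count is meant.** The final rule is stated as accepting a null hypothesis about p, and p is defined in that paragraph at 6 months. A count used to test p is a count of the event that defines p. Amendment B is described as enlarging the cohort "while maintaining the statistical power for the primary endpoint of the study", and that endpoint is CR at 6 months in 9.3. Section 9.4 places 3-month response among the secondary endpoints. No section names CR at any time up to month 6 as a parameter, benchmark or endpoint.

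**The case for a change.** The strongest opposing case is that a decision rule should not need interpretation. The text in force uses one event for p and another for the counts, and does so three times. The error can only favour the treatment, a few words would remove it, and one sentence in the report could say which count was used. The reassurance in 2.9.2 is also limited: it is interim, covers Cohort 2 only, and describes blood counts rather than CR status.

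The wording point stands, and 2.9.2 does not prove that the two counts agree. The rest does not carry. The literal reading needs 9.3's non-responder rules to govern the Simon count while 9.3's own endpoint, CR at 6 months, does not. If 9.3 governs, the gap closes. If it does not, a CR followed by dropout would count as well, a reading that nobody would defend. Nor would rewording alter a past stage-1 decision: 2.9.2 shows Cohort 1 full and Cohort 2 at 26 of 31 in September 2014, section 2.9.1 puts final Cohort 2 enrolment at 31, and 2.9.3 says the Extension Cohort followed completion of Cohort 3. Asking which count was used is a question for the results report.

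**Conclusion.** This is a clerical slip that needs no change to the plan. The counts in 9.1 are loosely worded, but the definition of p, the benchmark, the cohort table and 9.3 all point to CR at the 6-month evaluation, and an analyst would count that. On that count the design performs as stated, with type I error 3.05% and power 86.5%. Sample size, cut-offs and power would be the same under tidier wording.

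The conclusion rests first on the documents fixing the meaning. The transient-CR figures are assumptions and serve only as a bound: the literal reading breaches 5% only if more than about 1.1 points of subjects, roughly one counted CR in ten when the month-6 rate is 10%, gain and lose a CR before month 6 without another non-response event. Nothing in the documents supports a rate that high, or any effect on the stopping or activity decisions.
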